11.0 BIOSTATISTICS

11.0 Statistical Consideration

11.1 Study Design/Endpoints

This is a prospective study. The primary endpoint is safety of the procedure negative prostate biopsy rate at six months. The secondary endpoint is quality of life and safety of the procedure.

11.2 Sample Size/Accrual Rate

This is a pilot study so the sample size justification is based on providing reasonable precision of the primary efficacy endpoint, the negative biopsy rate at 6 months after focal bipolar RFA. We estimated the negative biopsy rate at 6 months after focal bipolar RFA is greater than or equal to 90%. If the negative biopsy rate at the 6-month visit is 90%, a sample size of 20 patients provides a two-sided 95% confidence interval of 68.3-98.8%. If the negative biopsy rate at the 6-month visit is 95%, the 95% corresponding confidence interval is 75.1-99.9%. Thus, the total sample size for this study will be 20 patients. We estimate an accrual rate of 4 patients a month. We anticipate completion of this study over a one year time period.

11.3 Stratification Factors

No stratification factors will be applied.

11.4 Analysis of Primary Endpoint

Descriptive statistics will be used to summarize patients' demographic and clinical characteristics collected at each visit. Mean, standard deviation and range will be calculated for continuous variables, and frequency and percentage will be generated for categorical variables. The primary objective is to assess the local oncologic efficacy of focal RFA in men with low-risk prostate cancer. The primary efficacy endpoint is negative biopsy rate at 6 months after focal bipolar RFA. The point estimate and its 95% confidence interval will be calculated using the exact binomial method.

11.5 Analysis of Secondary Endpoints

The secondary objective is to evaluate the change from baseline in quality-of-life indicators following focal RFA in patients with low-risk localized prostate cancer. The patients will complete the EPIC, AUA, RAS, and IIEF-5 questionnaires at baseline, 3- and 6-month visit. The QOL will be primarily based on the EPIC, developed to measure health related quality of life among men with prostate cancer. The EPIC assesses the disease-specific aspects of prostate cancer and its therapies and comprises four summary domains (Urinary, Bowel, Sexual and Hormonal) [Wei et al, 2000]. The EPIC summary score and subscale characteristics at each time-point will be calculated based on its scoring instruction (<http://roadrunner.cancer.med.umich.edu/epic/epicmain.html>). The summary score of the AUA, RAS and IIEF-5 questionnaires will be also calculated. Descriptive statistics (mean, median, standard deviation and inter-quartile range) will be

applied to summarize the QOL scores at each time-point and the score change between the 3- or 6-month visit and baseline. The normal distribution assumption of these score changes will be evaluated. The QOL score change from baseline will be evaluated using either the paired t-test if the original or transformed data are normally distributed, or the Wilcoxon signed-rank test whenever the normality assumption cannot be justified.

For safety analyses, the definitions of adverse event and serious adverse event were listed in Section 8.0. adverse event will be summarized by worst NCI CTCAE version 4.0 grade and serious adverse event will be listed separately. Safety data, such as toxicity and laboratory test, will be summarized by time point of collection. Descriptive statistics will be calculated for quantitative safety data and frequency counts will be summarized for classifications of qualitative safety data.

The image characteristics will be summarized using descriptive statistics. Mean, standard deviation and range will be calculated for continuous variables, and frequency and percentage will be generated for categorical variables.

Analysis of Tertiary Endpoint

The tertiary objective is to assess the potential health economic impact of focal RFA through the collection of medical resource utilization (MRU) data. Patients will collect weekly data on health care visits including clinician seen, indication for visit and any procedures associated with the visit. Descriptive statistics will summarize the frequency of visits by indication and will consider both visits captured in the MRU form as well as data collected on the adverse event form.

Cost values will be assigned to health care visits based on the indication and procedures/evaluations completed as a part of the visit. These costs will be assigned throughout the 6 month duration of the study to estimate the average cost of MRU after focal RFA.

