After enrollment, patients will undergo endo-rectal, multi-parametric 1.5 Tesla MRI with Dynamic contrast enhancement and Diffusion Weighted images. Areas on MRI that have a high level of suspicion for prostate cancer will be identified (right or left, Central or peripheral gland) and categorized from 1 Negative to 5 highly suspicious.

For study purposes, the prostate is divided into four regions: RIGHT CENTRAL, RIGHT PERIPHERAL, LEFT CENTRAL and LEFT PERIPHERAL. Patients must meet the original entry criteria on this repeat mapping biopsy and have unilateral prostate cancer. If the patients meet the mapping-biopsy enrollment criteria, they are treated with **focal bipolar radiofrequency ablation (RFA)** meaning RFA of the sites where the biopsies were positive but no more than one prostate side. Efficacy is defined as negative biopsy cores at the sites of the focal ablation on repeat extended biopsies at 6 months after RFA. A second MRI will be performed just prior to the 6 month repeat saturation biopsy performed identical to the original pre-treatment biopsy.

At baseline (prior to pre-treatment biopsy) and at 6 months (prior to the repeat biopsy used to define efficacy) the patient will complete an American Urologic Association lower urinary tract symptom score assessment (AUA score), Rectal Assessment Scale (RAS), International Index of Erectile Function (IIEF-5), and the EPIC quality of life questionnaires.

Following completion of the focal prostate radio-frequency ablation study at 6 months from treatment, patients will undergo standard/routine care including serum PSA level every 6 months and as needed digital rectal examinations; any future prostate biopsies will be performed at the discretion of the treating physician.

Patients will also be required to complete a medical resource utilization (MRU) form to capture resource utilization between study visits, which can be used to estimate costs associated with procedure related complications and health care visits. Patients will be requested to complete a weekly diary of medical resource utilization to limit recall bias that may occur between study visits.

SCHEMA

SCHEDULE OF EVALUATIONS / STUDY CALENDAR

Parameter	Prestudy	Week 0	Week 6	3 months	6 months	End of Study Visit
History	X					
Physical examination including DRE	X		X	X	X	
QOL questionnaires (EPIC,IIEF,AUA,RAS)	X				X	
MRU (Recording weekly by patients; collected at the following visits by study coordinator)			X	X	X	

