1.0 OBJECTIVES AND SCIENTIFIC AIMS

Primary Objective: To assess the local oncologic efficacy of focal RFA in men with unilateral, clinically localized prostate cancer as measured by the ability to obtain all negative biopsy cores at the sites of focal ablation of the cancer, “all negative” means no prostate cancer; if the biopsy contains inflammation, or pre-cancerous changes (high-grade prostatic intraepithelial neoplasia and /or atypical small acinar proliferation it will be considered negative for study purposes).

Secondary Objective: To evaluate the safety of the procedure and change in quality-of-life indicators from baseline to 6 months following focal RFA in patients with localized

prostate cancer. To understand and evaluate imaging characteristics of treated prostate cancer by bipolar RFA.

Tertiary Objective: To assess the potential health economic impact of focal RFA based on medical resource utilization data.

BACKGROUND AND RATIONALE

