
The mechanism of action of bipolar RFA is complex. It has been proposed that RFA exerts its efficacious effect by: (1) the induction of protein denaturation by thermocoagulation (2) the rupture of cell membranes from heating, (3) the transfer of water from intracellular to extracellular spaces, (4) vascular stasis, and (5) the induced apoptosis. The introduction of ultrasound guidance and the bi-polar design of the probe, allowed the heating process to be controlled and monitored in real time.

PRIMARY OBJECTIVE

This protocol will investigate the role of focal bipolar RFA in a defined prostate cancer population examining treatment efficacy (elimination of the cancer) based on repeat biopsy at six months from treatment.

SECONDARY OBJECTIVES

1. Changes from baseline in quality-of-life.
2. Image characteristics of treated prostate cancer by bipolar RFA
3. To evaluate the safety of the procedure

TERTIARY OBJECTIVE: Evaluate the health economic impact of focal RFA.

OVERVIEW OF STUDY DESIGN/INTERVENTION

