3.1 Imaging

After the informed consent is signed, the patient will be scheduled for an MRI (dynamic contrast enhanced and diffusion weighted imaging using a 1.5 Tesla endorectal MRI. The regions where both imaging sets indicate the potential for disease will be identified and categorized to one or more of 4 possible regions of the prostate as defined below.

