3.2 Mapping Prostate Biopsy

Transrectal ultrasound-guided prostate biopsies will be performed to determine study eligibility as well as to assess treatment efficacy. The two biopsy sessions (one pre-treatment and the other 6 months after focal RFA) will follow the same method. The rational for a complete mapping biopsy after RFA, rather than just sampling of the regions that were treated, is to identify cancer lesions not found in initial MRI/biopsy (thus, not treated) or cancer that may have developed after RF treatment.

Preparation/anesthesia: The patient will be given a Fleet enema prior to the procedure and administered prophylactic antibiotics. With the patient in the lithotomy position and under general anesthesia, transperineal saturation biopsies are obtained and separated in four sections: RIGHT CENTRAL, RIGHT PERIPHERAL, LEFT CENTRAL and LEFT PERIPHERAL.

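### Section 11.5 summarizes MRI findings without reference to biopsy, so the imaging objective can be met only as an unreferenced description

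*Combined protocol and SAP*

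**What the plan says.** The secondary objective in Section 1.0 includes the aim "To understand and evaluate imaging characteristics of treated prostate cancer by bipolar RFA". The later numbered list of secondary objectives shortens this to "Image characteristics of treated prostate cancer by bipolar RFA". Neither states an accuracy, agreement or prediction target.

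The design puts MRI and biopsy on one map:

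- In the protocol summary, suspicious MRI areas are located by side and by central or peripheral gland, and are "categorized from 1 Negative to 5 highly suspicious".
- Section 3.1 says regions with potential disease "will be identified and categorized to one or more of 4 possible regions of the prostate".
- Section 3.2 says "transperineal saturation biopsies are obtained and separated in four sections: RIGHT CENTRAL, RIGHT PERIPHERAL, LEFT CENTRAL and LEFT PERIPHERAL", and that both biopsy sessions follow the same method.
- For follow-up, the summary says "A second MRI will be performed just prior to the 6 month repeat saturation biopsy". The closing text of Section 1.2 says the repeat procedures are done as before treatment and that the biopsy covers the whole prostate.

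The whole imaging analysis is in Section 11.5: "The image characteristics will be summarized using descriptive statistics", followed by "Mean, standard deviation and range will be calculated for continuous variables, and frequency and percentage will be generated for categorical variables". The same section asks for quality-of-life scores at each time point and as change from baseline, and for safety data by time point. It asks for neither in the imaging analysis.

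**The concern.** What one wants to learn from an MRI of ablated tissue is what a suspicious signal means: residual cancer, or the effect of the ablation. Only the biopsy of the same tissue can answer that. The trial obtains that biopsy shortly after the MRI, in the same four regions, but the plan never sets the two side by side. It reports how often each MRI category occurs and, separately, how often the biopsy is negative.

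At stake is the use made of the second MRI. It has no other specified role in the analysis: Section 1.2 mentions it in connection with the primary endpoint, but efficacy is decided by the biopsy cores alone. If the comparison is made later without a plan, the region rule and any cut-off on the 1 to 5 scale could be chosen after the results are seen.

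**Working it through.** **Inputs.** From Sections 11.2 and 11.4: 20 patients, an assumed negative-biopsy rate of 90% (95% as the alternative), and exact binomial intervals. From the summary and Sections 3.1 and 3.2: four regions and a 1 to 5 MRI score. From Section 1.2: ablation of the cancer-bearing regions on one side, hemi-ablation if several areas are involved, and a stopping rule at more than 4 positive biopsies in the ablated area. The MRI counts, sensitivities and within-patient correlations below are my assumptions.

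**1. The plan's own figure.** The exact (Clopper-Pearson) limits are the 2.5% quantile of Beta(x, n−x+1) and the 97.5% quantile of Beta(x+1, n−x). For 18/20 this gives 68.3-98.8%, and for 19/20 it gives 75.1-99.9%. Both match Section 11.2. No precision figure is given for imaging.

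**2. Margins do not fix the joint table.** Take one result per man at the ablated site, with 4/20 suspicious and 2/20 biopsy-positive. Three joint tables have exactly these margins:

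| Positive sites that look suspicious | Sensitivity | Positive predictive value | Specificity |
|---|---|---|---|
| 2 | 2/2 = 100% | 2/4 = 50% | 16/18 = 88.9% |
| 1 | 1/2 = 50% | 1/4 = 25% | 15/18 = 83.3% |
| 0 | 0/2 = 0% | 0/4 = 0% | 14/18 = 77.8% |

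The marginal summaries are the same in all three rows.

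**3. What a cross-tabulation could deliver at 6 months** (all 20 men evaluable, one result each).

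- Expected positives and chance of none: at a 90% negative rate, 20 × 0.10 = 2, and 0.90^20 = 12.2%. At 95%, 1 and 0.95^20 = 35.8%. At 80%, 4 and 0.80^20 = 1.2%.
- Sensitivity, exact 95% interval (lower limit 0.025^(1/n) when all n are detected): 2/2 gives 15.8-100%, 1/2 gives 1.3-98.7%, and 4/4 gives 39.8-100%. At 5 positives, the count that triggers the stopping rule, 5/5 gives 47.8-100%.
- Specificity: 18/18 gives 81.5-100%, and 16/18 gives 65.3-98.6%.

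**4. Region counts.** If every region is scored in every man, there are 20 × 4 = 80 region pairs per time point. Because of hemi-ablation, the ablated regions number between 20 × 1 = 20 and 20 × 2 = 40, leaving 60 to 40 untreated. Regions within a man are not independent. With design effect 1 + 3ρ, the effective number is 80/(1 + 3ρ), which is 80, 62, 42 and 32 for assumed ρ of 0, 0.1, 0.3 and 0.5.

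At baseline the treated men supply 20 to 40 positive regions. An assumed sensitivity of 80% would then have an interval of 56.3-94.3% (16/20) to 64.4-90.9% (32/40), before allowing for clustering.

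**5. Interval method.** A patient-level bootstrap, the usual device for clustered regions, fails here. With 2/2 detected, every resample that contains a positive man gives 100%, so the interval has zero width. A share (18/20)^20 = 12.2% of resamples contains no positive man and gives no estimate. Exact intervals on one result per man avoid both problems.

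**The case against.** The best reply is that this is a 20-patient pilot whose objective is worded as description. A reader might infer from the gap that the imaging objective cannot be answered at all, or that the second MRI yields nothing. The documents do not support that. Frequencies of MRI findings before and after ablation satisfy the literal wording, and Section 11.5 does not forbid tabulating by region, visit or biopsy result. Its fault is that it asks for none of these.

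A reader might also infer that 80 scored region pairs per visit are already secured. That goes beyond the text. The 1 to 5 score and the assignment to regions are written out for the enrollment MRI only, and they speak of suspicious areas rather than a score for each of four regions. Use of the same scoring at 6 months is an inference from the statement that the repeat procedures match the pre-treatment ones. Registration of ultrasound to MRI is described only for the initial biopsy. So the scoring rule has to be stated before the table can be relied on.

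Finally, the added table cannot settle how well MRI detects residual cancer, as step 3 shows. That part of the reply stands in full. It limits what the table can claim, but it does not justify leaving MRI and biopsy unlinked.

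**Conclusion.** The point holds as a low-severity improvement. As planned, the imaging results will describe MRI appearance without a biopsy reference, and they cannot separate residual cancer from treatment effect in an ablated region.

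The gain from linking the two is real but modest. Specificity at 6 months could be described with moderate precision (for example 81.5-100% at 18/18), and the baseline table would have 20 to 40 positive regions. Sensitivity at 6 months would be nearly uninformative at the assumed 90% negative rate. The baseline figures apply only to men selected for unilateral disease on biopsy. The primary endpoint is unaffected, and no figure in the plan is disputed.

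This rests on all 20 men being evaluable, on one combined result per man for the ablated site, and on the 6-month MRI being scored by region as at baseline.

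**What to change.** 1. In Section 3.1 (and Section 7.0 for the repeat scan), state that both MRIs are scored 1 to 5 for each of the four regions and read before the corresponding mapping-biopsy result is known.
2. In Section 11.5, add a cross-tabulation of MRI score by biopsy result per region, at baseline and at 6 months, separately for ablated and untreated regions. Add the change in score within ablated regions. Treat the score as ordinal and report counts.
3. For the ablated site, derive one result per man, for example the highest MRI score in the ablated area, with biopsy positive if any core there is positive, in line with the primary endpoint. Give exact binomial intervals at that level and no bootstrap. If sensitivity or specificity is quoted, name the cut-off in advance.
4. Label the table descriptive, and say that sensitivity is not estimable if no biopsy is positive.

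The cost is a scoring rule with a matching data field for the 6-month MRI, and one table. No procedure is added. The downside is the wide 6-month intervals, which the label should make plain.

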APPENDIX E

 ID: _____ - _____
 Site _____ Subject _____

 INITIALS: _____
 F _____ M _____ L _____

Medical Resource Utilization Patient Diary
Patient Instructions:

Please complete the form below weekly by providing detail on non-study related health care visits. If there were multiple visits within a single week, please list out each individual visit.

Date	Did you have a health care visit this week (Y/N)?	If yes, how many healthcare visits did you have this week, and where did you visit?	For each of the visits, who did you see during this visit? (e.g., nurse, physician assistant, or physician)	What was the primary reason for this visit?	Did the healthcare personnel say the visit was related to the RFA procedure ¹ (Y/N)?	What treatment did you receive during this visit, if any?
Week 1:						
Week 2:						
Week 3:						
Week 4:						
Week 5:						
Week 6:						
Week 7:						
Week 8:						
Week 9:						
Week 10:						
Week 11:						
Week 12:						

1. Note to MCC clinical coordinator: If the patient's response to this question is "Y" an AE form must also be completed.

ID: _____ - _____
Site _____INITIALS: _____
F _____ M _____ L _____

Medical Resource Utilization Patient Diary

Patient Instructions:

Please complete the form below weekly by providing detail on non-study related health care visits. If there were multiple visits within a single week, please list out each individual visit.

Date	Did you have a health care visit this week (Y/N)?	If yes, how many healthcare visits did you have this week, and where did you visit?	For each of the visits, who did you see during this visit? (e.g., nurse, physician assistant, or physician)	What was the primary reason for this visit?	Did the healthcare personnel say the visit was related to the RFA procedure ¹ (Y/N)?	What treatment did you receive during this visit, if any?
Week 13:						
Week 14:						
Week 15:						
Week 16:						
Week 17:						
Week 18:						
Week 19:						
Week 20:						
Week 21:						
Week 22:						
Week 23:						
Week 24:						

1. Note to MCC clinical coordinator: If the patient's response to this question is "Y" an AE form must also be completed.

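### The costing rule uses the evaluations done at each visit, but the Appendix E diary does not prompt for tests, imaging or nights in hospital, so the average cost may be understated

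*Combined protocol and SAP*

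**What the plan says.** The text under Analysis of Tertiary Endpoint, at the end of Section 11.5, describes the data as follows: "Patients will collect weekly data on health care visits including clinician seen, indication for visit and any procedures associated with the visit". Visit frequency by indication is then summarised, and that summary "will consider both visits captured in the MRU form as well as data collected on the adverse event form". The costing step comes next: "Cost values will be assigned to health care visits based on the indication and procedures/evaluations completed as a part of the visit". Costs are accumulated over the six months of the study to give an average cost after focal RFA.

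The instrument is the diary in Appendix E, which instructs the patient: "Please complete the form below weekly by providing detail on non-study related health care visits". Besides the date, it asks whether there was a visit and who was seen, and then:
- "If yes, how many healthcare visits did you have this week, and where did you visit"
- "What was the primary reason for this visit"
- "Did the healthcare personnel say the visit was related to the RFA procedure"
- "What treatment did you receive during this visit, if any"

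A footnote tells the coordinator to complete an adverse event form when the patient answers yes to the question on relation to RFA.

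**The concern.** The costing rule has two inputs: the indication, and the procedures or evaluations carried out. The diary collects the first directly. It collects the second only as far as the patient regards what was done as treatment. A patient who had a scan, a culture or a blood test has no prompt to report it, and a patient who was admitted is not asked for how long.

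What is at stake is the average cost, which is the main product of the tertiary objective. The protocol's opening summary says the resource-use data can serve to estimate the cost of complications and visits, and Section 3.4 says they will support a health economic evaluation of the device. The opening summary also gives limiting recall bias as the reason for a weekly diary, so asking patients later for the missing detail would work against that aim. Section 13.2.1 has the linking key destroyed once analysis is complete, so the records cannot be consulted after that.

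**Working it through.** The plan gives no cost figure to reproduce, so the check compares the costing inputs with the diary columns.

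| Item relevant to costing | Where the diary can hold it | Prompted? |
|---|---|---|
| Indication | Primary-reason column | Yes |
| Clinician seen | Clinician column | Yes |
| Number and place of visits | Number-and-place column | Yes; can reveal a hospital, but not the length of stay |
| Therapeutic procedure | Free-text treatment column | Indirectly |
| Laboratory tests, imaging, other evaluations | No column | No |
| Nights in hospital | No column | No |

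The form also prints one row per week and asks the patient to list several visits inside it, so the detail of separate visits may be hard to keep apart.

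**Other possible sources**

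1. *Adverse event form.* Section 11.5 names it in the sentence on visit frequency and does not repeat it in the costing sentence. From the diary it is triggered only by a yes on relation to RFA. Its fields are not shown.
2. *Serious adverse event reporting.* Section 8.0.2 makes inpatient hospitalization a criterion, so admissions should come to light. The number of nights is not stated as a data item.
3. *Record review.* Section 13.0 lists abstraction among the coordinator's duties, and Section 13.2.4 describes review of the Cancer Center's own database. Neither is tied to the resource-use data, and visits made elsewhere may not be in that database.

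So no instrument shown or named for the costing step collects evaluations or length of stay.

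**Direction and size**

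Suppose that a share *s* of true cost comes from tests, imaging and bed-days, that a fraction *c* of that share is recovered from free text or the adverse event form, and that the rest is costed at zero. The understatement is then *s*(1 − *c*). Neither *s* nor *c* is in the documents; the values below are assumptions.

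| *s* | *c* = 0 | *c* = 0.5 | *c* = 1 |
|---|---|---|---|
| 20% | 20% | 10% | 0% |
| 50% | 50% | 25% | 0% |
| 80% | 80% | 40% | 0% |

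The result runs from 0% to 80% with the assumptions alone. The table shows what the answer depends on and is not an estimate.

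**The case against.** Three stronger readings are tempting, and the documents support none of them.

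*That the diary has no place for procedures.* The free-text treatment column can hold a therapeutic procedure, and the place column can show a hospital. The gap is confined to diagnostic work and length of stay.

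*That the cost estimate is biased low.* The plan costs on indication as well as on what was done, so a typical work-up could be assigned from the indication. It does not say that missing detail counts as zero. The diary also takes in visits that have nothing to do with RFA, which could raise the average if it is read as the cost of RFA. The net direction is therefore not established.

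*That the loss falls mainly on complication visits.* These are the visits with a second source. A visit reported as RFA-related requires an adverse event form, an admission is a serious adverse event, and Section 7.0 has toxicity assessed at week 6, 3 months and 6 months. The diary may be thinnest for unrelated visits, which matter least to the cost of RFA.

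It can also be said that the coordinator's duties and the data-query process leave room to recover detail. That is true, but nothing directs anyone to do so for resource use. After all these points the mismatch remains: evaluations are a stated costing input, and no specified form asks for them.

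**Conclusion.** The point holds in a narrow form. Section 11.5 costs visits partly on the evaluations completed, while Appendix E does not prompt for tests, imaging, other evaluations or nights in hospital, and no other source is assigned to the costing step. The average cost may be understated, on the condition that unrecorded items are costed at zero and are not recovered elsewhere. The size cannot be derived from the documents. The conclusion assumes that the adverse event form, which is not reproduced, does not already collect these items for costing.

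The priority is low. The endpoint is tertiary and descriptive, in a single-arm pilot of 20 patients, and the primary analysis is unaffected.

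**What to change.** In Appendix E, use one line per visit and add three separate entries:
- (a) tests, imaging or procedures done, each listed;
- (b) emergency visit (Y/N);
- (c) number of nights in hospital.

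The entries should stay separate, because one combined yes/no column would give neither the type of test nor the number of nights that costing needs. The coordinator should check them against available records and the adverse event form when the diary is collected at week 6, 3 months and 6 months, which are visits already in the study calendar.

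In the tertiary analysis text of Section 11.5, state that adverse event form data feed the costing step as well as the frequency summary. A sentence on the source of unit costs and on how a visit with missing detail is costed would settle the question of direction.

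The cost is a reprinted form and a little coordinator time for 20 patients.
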